2.4.2. Secondary Endpoints

Secondary outcomes and their endpoints are outlined in table 1 and 2. The secondary fall outcomes will be collected using the fall calendars for 12 months. The fall-related risk factor outcomes will be collected at the pre- and post-training test and the 26- and 52-week follow-up.

3. Study Design

This study is designed as an assessor-blinded, randomised, parallel-group (1:1 ratio), controlled trial

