5.1 Missing data

The number of missing observations and the associated reasons will be reported. For the primary outcome, fall rates, missing data will not be imputed; however, the analysis will be adjusted for follow-up time (days of follow-up will be used as an offset). Likewise, missing data regarding the secondary binary outcomes will neither be imputed, but the modified Poisson regression will be adjusted for person-years (days of follow-up will be used as an offset). For participants who do not return any fall calendars 0 falls and 0 person-years will be registered. However, if more than 10% of data is missing in any outcomes, a sensitivity analysis utilising multiple imputations will be conducted.

Missing data in continuous outcome are expected to be missing at random; thus, they will not be imputed as it has shown that multiple imputations do not add any benefits to a linear mixed-effects model.[25]

6. Statistical Analysis

All statistical tests will be performed using an intention-to-treat approach. Moreover, a per-protocol analysis will also be performed, including only participants who complete 75% or more of the training sessions. The secondary outcome will not be adjusted for multiple comparisons; thus, these results should be considered exploratory.

Count data will be reported as incidence rate ratios (IRR) with 95% confidence intervals (95% CI). Binary outcomes will be reported as risk ratios (RR) and 95% CIs. When appropriate, continuous variables will be reported as either mean and standard deviation or median and interquartile range.

Table 1 Variables, measures, and methods of analysis for fall outcomes.

Primary outcome					
Variable/outcome	Mode of assessing	Time frame	Variable type	Assumption	Methods of analysis
Fall rate (falls per person-year)	Fall calendars	Continuously for 12 months	Count	Equal mean and variance *	Poisson regression Alternative: Bootstrapping [†]
Secondary fall outcomes					
Variable/outcome	Mode of assessing	Time frame	Variable type	Assumption	Methods of analysis
Proportion of fallers	Fall calendars	Continuously for 12 months	Binary	Equal mean and variance *	Poisson regression with robust error variance
Time to first fall	Fall calendars	Continuously for 12 months	Survival	Linear relationship between log hazard and covariate ^a	Cox proportional hazard

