Laboratory-induced trip falls	Visual inspection of video recording of a level 1 trip perturbation; fall (1) or no fall (0)	Pre-training test; post-training test; 26- week follow-up; 52-week follow-up	Binary	-	Fisher's Exact

* Similarity of the calculated mean and variance; † If mean is not equal to variance; ^a Visual inspection of residual plots; [‡] Examined by visual inspection of histograms and QQ-plots; [‡] If data is not normal-distributed; ^o Participants ID as randoms effect - only participants, who did not fall during the perturbation at pre-training test was included

Table 2 Variables, measures, and analysis methods for fall-related risk factors.

Variable/outcome	Mode of assessing	Time frame	Variable type	Assumption	Methods of analysis
Single- and dual-task gait speed	6-meter walking test; walking speed (m/s)	Pre-training test; post-training test; 26- week follow-up; 52-week follow-up	Continuous (ratio)	Normal distribution of residuals and random effects ^{*‡} Homogeneity of variance [‡]	Linear mixed-effects model ^o

Single- and dual-task sway	30-second balance test on WBB [†] ; centre of pressure area (mm ²) and velocity (mm/s)	Pre-training test; post-training test; 26- week follow-up; 52-week follow-up	Continuous (ratio)	Normal distribution of residuals and random effects * [◊] Homogeneity of variance [◊]	Linear mixed-effects model [○]
Choice stepping reaction time (CSRT)	CSRT on WBB [†] ; reaction time (ms)	Pre-training test; post-training test; 26- week follow-up; 52-week follow-up	Continuous (ratio)	Normal distribution of residuals and random effects * [◊] Homogeneity of variance [◊]	Linear mixed-effects model [○]
Short physical performance battery	2x4 meter walking time, 3x10 second static balance with 3 different foot positions, and 5 chair raises; score from 0-12 (higher score indicates better performance)	Pre-training test; post-training test; 26- week follow-up; 52-week follow-up	Continuous (ordinal)	Normal distribution of residuals and random effects * [◊] Homogeneity of variance [◊]	Linear mixed-effects model [○]
Trial-making-test Part A and B; time and error	Part A and Part B of the Trail-making-test; time (s) and errors (n). Difference in time-to-complete between Part A and Part B; time (s)	Pre-training test; post-training test; 26- week follow-up; 52-week follow-up	Continuous (ratio)	Normal distribution of residuals and random effects * [◊] Homogeneity of variance [◊]	Linear mixed-effects model [○]

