6.3. Major Protocol Deviations

Major protocol deviations will be reported in the trial registration at ClinicalTrials.gov ([NCT04733222](https://clinicaltrials.gov/ct2/show/NCT04733222)), the local ethics committee, and the SAP.

7. Implementation of Analysis Plan

The data will be exported from REDCap to the statistical program STATA. An external statistician not involved in the study will assist with the statistical test.

STATA CODE

Poisson regression (example of code for fall rate):
poisson fallrate ib1.group, irr exposure(personyear)

Poisson regression with bootstrapping (example of code for fall rate):
poisson fallrate ib1.group, irr exposure(personyear) vce(bootstrap, reps(1000))

Poisson regression adjusting for age, sex, and fall history (example of code for fall rate):
poisson fallrate ib1.group age i.sex i.prev_faller, irr exposure(personyear)

Poisson regression with robust error variance (example of code for proportion of fallers):
glm faller ib1.group, fam(poisson) link(log) vce(robust) eform

Poisson regression with robust error variance adjusting for age, sex, and fall history (example of code for proportion of fallers):
glm faller ib1.group age i.sex i.prev_faller, fam(poisson) link(log) vce(robust) eform

Cox survival analysis (example of code for time to first fall):
stset firstfall, failure(faller==1)
stcox group

Cox survival analysis adjusted for age, sex, and fall history (example of code for time to first fall):

```
stset firstfall, failure(faller==1)  
stcox group age i.sex i.prev_faller
```

unpaired t-test (example of code for Global Patient Impression of Change (gpic)):

```
ttest gpic, by(group) unpaired
```

Unpaired two-sample Wilcoxon test (example of code for Global Patient Impression of Change):

```
ranksum gpic, by(group)
```

Fisher's exact (example of code for the proportion of fallers following slip perturbation at pre-training (t1)):

```
tabulate lab_slip_t1 group, exact
```

Linear mixed-effects model (example of code for single-task gait speed):

```
mixed gaitspeed_st group time || record_id:, var reml
```

In case of significant interaction effect, a posthoc analysis adjusted using the Bonferroni method is employed using the following code:

```
contrast rb1.time#group, mcompare(bonferroni)
```

Linear mixed-effects model adjusting for age, sex, and fall history (example of code for single-task gait speed):

```
mixed gaitspeed_st age i.sex i.prev_faller group##time || record_id:, var reml
```

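### For time to first fall, Table 1 checks log-linearity, which cannot fail for a two-level group variable, and never checks proportional hazards, on which the single hazard ratio relies

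*Combined protocol and SAP*

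**What the plan says.** In section 6, the Table 1 row for time to first fall names the method as "Cox proportional hazard" and gives a single assumption, "Linear relationship between log hazard and covariate". The footnote attached to it gives the check: "Visual inspection of residual plots". The type of residual is not stated. The row offers no alternative method.

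The Stata code in section 7 gives the main analysis as "stset firstfall, failure(faller==1) stcox group", so group is the only covariate. The adjusted sensitivity analysis is "stcox group age i.sex i.prev_faller", which adds age as a continuous term, sex and fall history. Neither is followed by a proportional-hazards test, a log-log plot, a group-by-time term or a split of follow-up time.

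Two further statements set the context. Section 2.4.2 fixes the length of follow-up: "The secondary fall outcomes will be collected using the fall calendars for 12 months". Section 6 fixes the standing of the result: "The secondary outcome will not be adjusted for multiple comparisons; thus, these results should be considered exploratory".

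**The concern.** The assumption column in Table 1 should name what each model needs in order to be read as intended. For this row it names a condition that the main model satisfies automatically and leaves out the one that carries the interpretation. The residual plots could therefore be inspected and reported as satisfactory without anyone having looked at whether the hazard ratio is stable over the year.

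This matters because the intervention is short and falls are counted for 12 months. The synopsis presents durability as a possibility rather than an established fact. One HR over the year cannot separate a sustained effect from an early effect that fades. For a time-to-event outcome that difference is the main information added beyond the fall rate and the proportion of fallers.

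**Working it through.** **1. Can the listed check fail?** The main model is log h(t | g) = log h0(t) + βg, with g taking two values. A line through two points always fits, so log-linearity has no content here. In the adjusted model it has content for age only, since sex and fall history are entered as factors.

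**2. Inputs.** The SAP gives no figure for time to first fall, so the control hazard comes from section 3.1: fall rate 0.85, 50% reduction, 80% power, 5% significance, 20% dropout, 70 per group. Reading 0.85 as the control rate per person-year (two-sided test) reproduces the stated size:

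- n = (1.960 + 0.842)² × (0.85 + 0.425) / (0.85 − 0.425)² = 55.4, so 56 per group
- 56 / 0.8 = 70 per group

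The 12-month horizon is from section 2.4.2, and the design is "randomised, parallel-group (1:1 ratio), controlled trial". The patterns of change at month 6 are assumptions, not figures from the documents.

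**3. What the Cox model would return.** Let S0 and S1 be the fall-free curves, f0 = 0.85·S0, f1 = 0.85·HR(t)·S1, and G(t) the probability of still being followed. The large-sample estimate β solves

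∫₀¹ G(t)·[f1(t)·(1 − p(t)) − f0(t)·p(t)] dt = 0, where p = e^β·S1 / (e^β·S1 + S0).

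G = 1 means no loss; G = 0.8^t means 20% lost by 12 months. The PBT-arm 12-month risk is 1 − exp(−0.85 × mean of the two half-year HRs). Control risk is 1 − exp(−0.85) = 57.3%.

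| HR months 0–6, then 6–12 | PBT 12-month risk | Cox HR, no loss | Cox HR, 20% loss |
|---|---|---|---|
| 0.5, 0.5 | 34.6% | 0.50 | 0.50 |
| 0.3, 0.7 | 34.6% | 0.47 | 0.46 |
| 0.25, 1.0 | 41.2% | 0.56 | 0.54 |
| 0.5, 1.5 | 57.3% | 0.90 | 0.87 |

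The first two rows share a 12-month risk and nearly share an HR, so the planned output could not tell them apart. In the last row falls are delayed but no fewer people have fallen by 12 months, and the HR is still below 1.

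**4. What the extra displays would show.** Six-month risk in the PBT arm is 1 − exp(−0.85 × 0.5 × 0.5) = 19.1% under constant 0.5 and 1 − exp(−0.85 × 0.5 × 0.3) = 12.0% under 0.3 then 0.7. Kaplan-Meier curves display that difference. Restricted mean fall-free time to 12 months is the area under the curve:

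- Control: (1 − e^−0.85)/0.85 = 0.674 years = 8.08 months
- Constant 0.5: (1 − e^−0.425)/0.425 = 0.815 years = 9.78 months; gain 1.69
- 0.3 then 0.7: (1 − e^−0.1275)/0.255 + e^−0.1275·(1 − e^−0.2975)/0.595 = 0.850 years = 10.20 months; gain 2.12
- 0.5 then 1.5: (1 − e^−0.2125)/0.425 + e^−0.2125·(1 − e^−0.6375)/1.275 = 0.749 years = 8.99 months; gain 0.91

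Gains are taken before rounding. Each is a plain statement of average fall-free time gained and needs no proportionality.

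**5. Could a test be relied on to trigger a fallback?** In 3,000 simulated trials per scenario (70 per arm, 20% loss), a 5% trend test for non-proportionality rejected in 59% for 0.25 then 1.0, 41% for 0.35 then 1.0, 21% for 0.5 then 1.0 and 50% for 0.5 then 1.5. It rejected in 5% when the HR was constant. There were about 62 to 72 first falls per trial in the changing-effect scenarios. A non-significant test would say little.

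**The case against.** The strongest reply is that little hangs on this HR. Time to first fall is secondary and the secondary results are declared exploratory. The 12-month benefit is estimated by the primary fall rate and the proportion of fallers, and neither needs proportional hazards. An average HR over a fixed 12 months can be interpreted if it is reported as an average. All of this stands, and it limits the point to a minor one.

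It is also fair that the residual plots are of unstated type and might in practice include Schoenfeld plots. But the SAP ties them to log-linearity, so proportional hazards is not a planned check.

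Four stronger readings are tempting, and the documents do not support them:

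- **That the effect will wane.** The synopsis describes the training as potentially sustainable and likens its effect to vaccination. Nothing in the SAP predicts fading, so the consequence is conditional.
- **That this row alone lacks a fallback.** In Table 1 only the count outcomes and the Global Impression scale have an alternative. The binary fall outcomes have none either.
- **That the HR depends materially on who drops out.** Follow-up is fixed at 12 months, and at the SAP's own 20% loss the HR moves by only 0.01 to 0.03 in the patterns above.
- **That a significant test should switch the analysis.** At 70 per arm the test is too weak for that. HRs for the second half-year also rest only on people still fall-free, so they can drift when individual fall risk varies, even if the effect is constant.

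**Conclusion.** The point holds as a minor one. The assumption stated for the Cox model is the wrong one: the listed check cannot fail in the main analysis, and proportional hazards is neither named nor assessed. If the effect changed within the year, the reported HR would be an average that conceals it: about 0.47 for 0.3 then 0.7, 0.56 for 0.25 then 1.0, and 0.90 for 0.5 then 1.5 despite equal 12-month risk. These sizes rest on a control rate of 0.85 per year, constant hazards within each half-year, and assumed changes at month 6. A reader might infer that the trial's main conclusion is at risk. It is not, because the primary fall-rate analysis does not use this model.

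**What to change.** - In the Table 1 row for time to first fall, replace the assumption with proportional hazards, assessed by scaled Schoenfeld residuals and log-log plots, in both the unadjusted and adjusted models.
- Keep the linearity check only for age in the adjusted model, and name the residuals to be plotted.
- Report Kaplan-Meier curves by group and the difference in restricted mean fall-free time to 12 months, with its 95% confidence interval, beside the HR in all cases. Do not make them conditional on a test.
- If the plots suggest a changing effect, describe the HR as an average over 12 months. HRs for months 0–6 and 6–12 may be added, labelled descriptive.

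The cost is one table cell, a few lines of Stata code, a small amount of extra analysis and one more exploratory estimate. Data collection does not change.

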3.1. Sample Size

The sample size calculation was conducted in G*power (version 3.1.9.4, University of Kiel, Kiel, German) using a Poisson regression model. The calculation was made with certain assumptions (80% power, 5% significance level, 50% difference in fall rate (favouring the PBT), and 20% dropout rate) and an expected average fall rate of 0.85.[18–21] This resulted in an estimated required sample size of 70 participants in each group.

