Fall-related fracture rate	Fall calendars	Continuously for 12 months	Count	Equal mean and variance *	Poisson regression Alternative: Bootstrapping [†]
The proportion with a fall-related fracture	Fall calendars	Continuously for 12 months	Binary	Equal mean and variance *	Poisson regression with robust error variance
Fall-related injury rate (other injuries than fractures)	Fall calendars	Continuously for 12 months	Count	Equal mean and variance *	Poisson regression Alternative: Bootstrapping [†]

The proportion with fall-related injuries (other injuries than fractures)	Fall calendars	Continuously for 12 months	Binary	Equal mean and variance *	Poisson regression with robust error variance
Fall-related hospital contact rate	Fall calendars	Continuously for 12 months	Count	Equal mean and variance *	Poisson regression Alternative: Bootstrapping [†]
The proportion with a fall-related fracture	Fall calendars	Continuously for 12 months	Binary	Equal mean and variance *	Poisson regression with robust error variance
All-cause fracture rates	Fall calendars	Continuously for 12 months	Count	Equal mean and variance *	Poisson regression Alternative: Bootstrapping [†]
The proportion with an all-cause fracture	Fall calendars	Continuously for 12 months	Binary	Equal mean and variance *	Poisson regression with robust error variance
Patient Global Impression of Change	7-item questionnaire and 11-point Likert scale; proportion “4 – somewhat better”) and 0-11 points on the Likert scale (lower score indicates better performance)	52-week follow-up	7-item questionnaire: Binary VAS: Continuous (Ordinal)	VAS-scale: Normal distribution [‡] Homogeneity of variance [‡]	7-item questionnaire: Fisher’s Exact VAS-scale: Unpaired t-test Alternative: Unpaired two-sample Wilcoxon test [‡]
Laboratory-induced overall fall rate	Visual inspection of video recording of a level 1 slip and trip perturbation; fall (1) or no fall (0)	Pre-training test; post-training test; 26- week follow-up; 52-week follow-up	Count	Equal mean and variance *	Poisson regression Alternative: Bootstrapping [†]

Laboratory-induced slip falls	Visual inspection of video recording of a level 1 slip perturbation; fall (1) or no fall (0)	Pre-training test; post-training test; 26- week follow-up; 52-week follow-up	Binary	-	Fisher's Exact

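### Patient Global Impression of Change: the seven-level item is reduced to a binary outcome for Fisher's exact test with no stated reason; all levels should be analysed, with the responder proportion kept beside them

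*Combined protocol and SAP*

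**What the plan says.** The Patient Global Impression of Change row of Table 1 (SAP section 6) describes the measure as "7-item questionnaire and 11-point Likert scale; proportion “4 – somewhat better”) and 0-11 points on the Likert scale", collected at the 52-week follow-up. The row holds two measures of the same construct, and they are treated differently.

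- **Variable type:** "7-item questionnaire: Binary VAS: Continuous (Ordinal)".
- **Analysis of the graded item:** Fisher's exact test, and nothing else.
- **Analysis of the 11-point scale:** "VAS-scale: Unpaired t-test Alternative: Unpaired two-sample Wilcoxon test".

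The Stata code in section 7 already contains a rank test under this outcome's name, "ranksum gpic, by(group)". On status, section 6 says: "The secondary outcome will not be adjusted for multiple comparisons; thus, these results should be considered exploratory". The same section promises risk ratios with 95% CIs for binary outcomes.

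Two points of reading matter. The table speaks of seven items, not seven levels; a numbered, labelled level 4 and a proportion defined at it point to one response scale with seven ordered levels, but that is an inference. No comparison sign appears before the 4, and a closing bracket there has no partner, so text may have been lost in conversion from PDF. The cut is taken below as level 4 or above.

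**The concern.** Once the item is cut, all answers on the same side count as equal. A participant who moves between two levels below the cut, or between two above it, contributes nothing to the comparison. That can be a sound choice when a threshold has a clinical meaning, but the SAP cites no minimal important change, guideline or other ground for this one.

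It is also out of line with the rest of the plan. The Short Physical Performance Battery, the Short Falls Efficacy Scale and the EuroQoL in Table 2 are all labelled ordinal and analysed on their full range. The other outcomes given to Fisher's test, laboratory slip and trip falls, are naturally binary.

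At stake is the sensitivity of one secondary outcome. A real but moderate shift in participants' own rating could be reported as non-significant. The two measures in the row could also disagree only because they were analysed differently.

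**Working it through.** **Numbers per arm.** The SAP gives no sample size or power for this item, only for the primary outcome (section 3.1): "80% power, 5% significance level, 50% difference in fall rate (favouring the PBT), and 20% dropout rate" and "an expected average fall rate of 0.85", from which "This resulted in an estimated required sample size of 70 participants in each group". Taking 0.85 and 0.425 as the two rates and a two-sided test:

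n = (1.960 + 0.842)² × (1/0.85 + 1/0.425) / (ln 2)² = 7.849 × 3.529 / 0.4805 = 57.7, rounded up to 58; 58 × 1.2 = 69.6, rounded up to 70.

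The stated figure is reproduced. With 20% dropout, 70 × 0.8 = 56 per arm would have 52-week data, so 56 and 70 bracket the case.

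**Assumptions for the item.** Seven ordered levels arise from a latent normal variable shifted by d SD between arms. Five control distributions were used, with 15%, 30% (two shapes), 57% or 70% at level 4 or above. Tests are two-sided at 5%. None of this comes from the documents. The responder proportion in the shifted arm is Φ(Φ⁻¹(p) + d). For p = 0.30 and d = 0.5 this is Φ(−0.524 + 0.5) = Φ(−0.024) = 0.49. For p = 0.70 it is Φ(0.524 + 0.5) = Φ(1.024) = 0.85.

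**Power with 56 per arm, d = 0.5.**

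| Responders, control v shifted | Fisher on the cut | Rank-sum on seven levels | Gain (points) |
|---|---|---|---|
| 15% v 30% | 38% | 61% | 23 |
| 30% v 49% | 47% | 68-71% | 21-24 |
| 57% v 75% | 46% | 71% | 25 |
| 70% v 85% | 38% | 72% | 34 |

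**How much is the cut and how much is Fisher's test.** An uncorrected two-proportion test separates them. For 30% v 49% its power is about Φ[(0.19 − 1.96 × √(2 × 0.395 × 0.605/56)) / √((0.30 × 0.70 + 0.49 × 0.51)/56)] = Φ[(0.190 − 0.181)/0.0906] = Φ(0.10) = 54%; simulation gave 55%. Using 55%, Fisher's conservatism costs 55 − 47 = 8 points and the cut costs 68 − 55 = 13 to 71 − 55 = 16 points. For 70% v 85% the uncorrected test has 47%, so the split is 47 − 38 = 9 and 72 − 47 = 25. With no shift, rank-sum rejected 4.6-5.3% of the time and Fisher 2.5-3.3%.

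**Dependence on the size of the shift** (56 and 70 per arm, cut at 4 or above):

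| Shift | Gain of rank-sum over Fisher |
|---|---|
| 0.1 SD | 2-5 points |
| 0.2 SD | 7-11 points |
| 0.4-0.6 SD | 16-35 points |

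**A different model.** Under proportional odds, with odds ratios from 1.5 to 3.0, six control distributions and the cut at 4 or above, the gain is 9-44 points (median 19) with 56 per arm and 9-40 (median 18) with 70. Moving the cut to 5 or 6 gives 9-53 points overall. Fisher's conservatism accounts for about 3-10 points.

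**The reverse case.** Suppose the only effect is that 22% of participants move from level 3 to level 4. Fisher then has 57% power against 16% for rank-sum with 56 per arm, and 69% against 18% with 70.

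The figures are for the rank-sum test. They carry over approximately to the proportional-odds model, because its two-group score test is the Wilcoxon test.

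**The case against.** The strongest reply is that the row already handles the matter. The same construct is measured at the same visit on an 11-point scale, kept uncut, with a Wilcoxon alternative. A responder proportion next to a full-scale analysis also fits Table 1, which pairs fall, fracture and injury rates with the matching proportions. A proportion is easier to read than a common odds ratio, and a rank test alone gives no effect estimate. Secondary results are declared exploratory, and this outcome is not among the secondary objectives in section 2.2.

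Most of that stands. It limits the consequence and shows that the responder proportion should not be dropped. It does not supply a reason for using only one cut of the graded item: a second measure does not recover information discarded from the first.

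A reader might infer a fixed loss, such as 15-34 points of power. The documents do not support one. They give no distribution, no expected effect and no readable operator for the cut. The loss shrinks to a few points for small shifts, and the order reverses when the effect sits at the cut. Nor do they support reading the cut as data-driven, since it is written into the SAP.

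**Conclusion.** The point holds as a minor one. The graded item is reduced to a binary outcome with a single test and no stated reason, while comparable measures in the plan keep their scale. For a general shift, analysing all levels gains about 2-5, 7-11 or 16-35 points of power at 0.1, 0.2 or 0.4-0.6 SD, and some of that is due to Fisher's test rather than to the cut. These figures rest on assumed distributions, on seven ordered levels and on a cut at level 4 or above. They say nothing about which shift to expect a year after four training sessions. If the sponsor expects the effect at the threshold alone, the binary analysis is the better one, and that expectation is the reason the SAP should state.

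**What to change.** In Table 1, before the data are analysed:

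1. Change the type of the graded item from binary to ordinal, and confirm that it has seven ordered levels.
2. Analyse all levels with a proportional-odds model (`ologit` on the seven-level variable with group as covariate), reporting the common odds ratio with 95% CI. Use the Wilcoxon rank-sum test as a check that needs fewer assumptions.
3. Keep the responder proportion by arm beside it, with its risk ratio and 95% CI as section 6 promises. The robust Poisson code in section 7 already produces this for the proportion of fallers.
4. State the cut with its comparison sign and the reason for it.
5. In section 7, give the graded item and the 11-point scale separate variable names.

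The cost is one table row and a few lines of Stata, with no new data or participants. The downside is that a common odds ratio is less direct to read than a proportion and adds the proportional-odds assumption; the retained proportion and the rank test largely cover both.

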3.2. Randomisation and Blinding

After the pre-training tests, participants will be randomly allocated to either the PBT or treadmill walking group using a permuted block randomisation module in REDCap to ensure similar group sizes (Research Electronic Data Capture; version 9.5.6). Random block sizes (two, four, six, or eight) will ensure that allocation concealment is maintained. The allocation sequence will be generated by a research staff member not involved in enrolling or assigning participants to groups.

4. Study Population

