Short Falls Efficacy Scale	7-item questionnaire; score from 7-28 (lower score indicates better performance)	Pre-training test; post-training test; 26- week follow-up; 52-week follow-up	Continuous (ordinal)	Normal distribution of residuals and random effects * [◊] Homogeneity of variance [◊]	Linear mixed-effects model [○]

EuroQoL 5D-5L	
5-item questionnaire and visual analogue scale; index from 0-1 (higher score indicates better performance)
 
Visual analogue scale from 0-100 (higher score indicates better performance)
	
Pre-training test; post-training test; 26-week follow-up; 52-week follow-up
	
Continuous (ordinal)
	
Normal distribution of residuals and random effects^{*†} Homogeneity of variance[‡]
	
Linear mixed-effects model[○]

---------------	---	--	-----------------------------	---	---

* Examined by visual inspection of histograms and QQ-plots; [†] Examined by visually inspecting residuals plotted against fitted values; [‡] If data is not normal-distributed; [‡] Violations of assumptions will be noted; however, no alternative method will be used, as the linear mixed-effects model is robust against such violations; [○] Participant ID as the random effect

Sensitivity analysis

Fall outcomes

For the primary outcome (fall rates) and secondary fall outcomes, a sensitivity analysis adjusting for known confounders (age, sex, and previous falls) will be conducted to evaluate the robustness of the results. Furthermore, if the count variable data is over-dispersed, a poisons regression with bootstrapping will be performed; however, a sensitivity analysis without bootstrapping will also be carried out. These analyses were planned before the commencement of data collection. Additional fall rate sensitivity analyses 1) only including participants with no prior history of falls 12 months before study commencement and 2) only including participants with a history of falls 12 months before study commencement will also be conducted. These sensitivity analyses were planned after data collection began.

Fall-related risk factor outcomes

Before data collection commenced, it was determined to conduct a sensitivity analysis on the secondary fall-related risk factors adjusting for age, sex, and previous falls will be carried out.

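### An unattached Table 1 footnote limits an analysis to people who did not fall at the pre-training perturbation; applied to the laboratory-fall rows, it contradicts the rest of the SAP and costs power

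*Combined protocol and SAP*

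**What the plan says.** Table 1 in section 6 of the SAP lists three laboratory outcomes under secondary fall outcomes: an overall fall rate (slip plus trip), "Laboratory-induced slip falls", and the matching trip outcome. Each is scored from video and listed at the pre-training test, the post-training test, 26 weeks and 52 weeks. The overall rate is analysed by Poisson regression, with bootstrapping as the alternative. The slip and trip outcomes are analysed by Fisher's exact test.

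The last footnote under that table has two parts. It opens with "Participants ID as randoms effect" and continues that "only participants, who did not fall during the perturbation at pre-training test was included". Table 2 defines its own random-effect footnote, "Participant ID as the random effect", with no restriction attached.

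Three other places bear on this:

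- Section 6 opens by putting all statistical tests on an intention-to-treat basis.
- The only example code for laboratory falls is "tabulate lab_slip_t1 group, exact", for the pre-training visit and without a subset condition.
- Section 3.2 fixes the order of events: "After the pre-training tests, participants will be randomly allocated".

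**The concern.** Perturbation training exposes people to repeated slips and trips. A participant who falls at the pre-training perturbation and recovers from the same one later is the most direct evidence of learning that these outcomes can offer. A restriction to pre-training non-fallers removes all such participants.

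The SAP can also be read two ways. One analyst would follow the footnote and analyse a subset; another would follow section 6 and the code and analyse everyone. Both could claim to have followed the plan, and the choice could be made after the results are known. The sensitivity analysis section says whether its analyses were planned before or after data collection began, but nothing of the kind is said about this restriction.

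**Working it through.** **Which rows the footnote can govern.** Every Table 1 row other than the laboratory ones is based on fall calendars or on a 52-week questionnaire. Only the three laboratory rows involve a perturbation at a pre-training test. This is an inference from wording, because no row in the available text shows the marker.

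**What follows if it governs them.**

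- *Population.* Participants who fell before training are randomised but left out, against the intention-to-treat statement.
- *Time points.* For slip and for trip, the pre-training table has 0 falls in both arms by construction. The example code at t1 would then have nothing to compare.
- *Method.* Neither Fisher's exact test nor the Poisson code has a participant random effect, so half of the footnote has no counterpart in Table 1.
- *Combined outcome.* The overall rate uses a slip and a trip, but the footnote speaks of one perturbation. It does not say whether a fall on either, or only on both, excludes a participant.

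**Bias.** Pre-training fall status is measured before allocation, so it is a baseline variable. A subset defined by it is still compared as randomised. The cost is precision and a narrower population.

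**The plan's own figure.** Section 3.1 gives 70 per group for the primary outcome. With rates 0.85 and 0.425, two-sided 5% (sidedness assumed) and 80% power, the rate-difference formula gives n = (1.960 + 0.842)² × (0.85 + 0.425) / 0.425² = 55.4, so 56, and 56 / 0.8 = 70. The figure reproduces. It was not derived for laboratory falls and serves here only as the starting number per arm.

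**Size of the loss.** The documents give no laboratory-fall proportion, so all of the following is assumed: a proportion p falling before training of 20%, 40% or 60%; a training odds ratio of 0.3; the control risk at follow-up unchanged from before training; no laboratory dropout; and an exact Fisher test at 5%.

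- Number kept per arm = 70 × (1 − p): 56, 42 or 28.
- Equal individual risk: the control risk is p and the trained risk is 0.3·o / (1 + 0.3·o), with o = p / (1 − p). For p = 0.4, o = 0.667 and the trained risk is 0.2 / 1.2 = 0.167. The risks are the same among those kept.
- Varying individual risk: each person's logit is normal with SD 2, centred so that the mean risk is p. Among those kept, each person is weighted by the chance of not having fallen before training, so the risks are lower.

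| Individual risk | p | Kept per arm | Control vs trained, all | Power, all 70 | Control vs trained, kept | Power, kept |
|---|---|---|---|---|---|---|
| Equal | 20% | 56 | 0.200 vs 0.070 | 0.54 | 0.200 vs 0.070 | 0.42 |
| Equal | 40% | 42 | 0.400 vs 0.167 | 0.83 | 0.400 vs 0.167 | 0.59 |
| Equal | 60% | 28 | 0.600 vs 0.310 | 0.92 | 0.600 vs 0.310 | 0.47 |
| Varying | 20% | 56 | 0.200 vs 0.099 | 0.31 | 0.131 vs 0.054 | 0.17 |
| Varying | 40% | 42 | 0.400 vs 0.239 | 0.47 | 0.244 vs 0.115 | 0.26 |
| Varying | 60% | 28 | 0.600 vs 0.419 | 0.51 | 0.366 vs 0.194 | 0.21 |

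Power falls in every row, and a difference between arms remains in every row.

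**The case against.** The strongest reply is that the footnote may govern nothing in the current plan. No Table 1 row visibly carries its marker, although other markers survive in the same table. Its random effect belongs to a mixed model, and Table 1 has none. The pre-training time point, the unrestricted code and the intention-to-treat statement all suggest that the laboratory tests are meant for everyone. On this view the footnote is left over from a dropped analysis. That may be so, and a marker lost in reading the PDF is equally possible; the documents do not settle it. Either way the text stands in the SAP and has to be attached to an analysis or removed.

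A reader might also infer that the restricted analysis cannot show any benefit, because those kept can only stay the same or get worse. That is true of change within a person. The planned tests compare arms, and a participant who did not fall before training can fall later, so a benefit can appear as fewer falls than in the control arm.

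Two further points stand. Laboratory falls are absent from the list of secondary outcomes in section 2.2 and appear only in Table 1, and section 6 treats secondary results as exploratory. The primary outcome is not affected.

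**Conclusion.** The inconsistency is real and should be corrected. The footnote, applied to the only rows that it fits, contradicts the analysis population, a listed time point and the example code, and its model appears nowhere in Table 1.

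The documents do not support reading it as a settled decision to restrict the laboratory analyses, as a source of bias, or as making a benefit undetectable. If applied, it excludes every participant who could move from fall to no fall and it costs power. Under the assumptions above, the loss runs from 0.12 (0.54 to 0.42) to 0.45 (0.92 to 0.47) in absolute power. The true loss depends on a pre-training fall proportion that the documents do not give. The consequence is confined to secondary, exploratory outcomes.

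**What to change.** - Delete the restriction from the main laboratory-fall analyses. If it is kept, make it a labelled sensitivity analysis that names its rows and says how falling on the slip, the trip or both is handled for the combined outcome.
- Remove the random-effect wording from Table 1, or name the model that it belongs to.
- For slip and trip falls, analyse all randomised participants tested at each post-training visit, with pre-training laboratory-fall status as a covariate. The robust-error Poisson model that the SAP already uses for other binary outcomes would serve. It yields the risk ratios and 95% confidence intervals that section 6 promises for binary outcomes, which the planned Fisher's exact test does not give. Other models with the same adjustment would also be acceptable.
- Report pre-training laboratory falls by arm descriptively, without a test, and replace the t1 example code with code for a post-training visit.

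The cost is SAP wording and a few lines of code, using a measurement already scheduled for the pre-training test. The downside is one added covariate in a secondary, exploratory model. If an arm has no falls at a visit, the risk ratio cannot be estimated, and the counts with Fisher's exact test would be reported for that visit.
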